5.3. Dose Selection

Clinical and nonclinical safety and efficacy data support the selection of a once-daily 10 mg dose for the samidorphan component of ALKS 3831 in this study. In a prior study in alcohol-dependent subjects, samidorphan 10 mg showed the largest reduction in drinking behavior. Furthermore, clinical trial experience to date has shown samidorphan 10 mg to be well-tolerated.

This study includes a 2-week open label ALKS 3831 period. This open-label ALKS 3831 period is included because previous clinical studies have shown that the majority of AEs associated with samidorphan occur within the first 2 weeks of treatment. Starting all subjects on samidorphan not only establishes similar pharmacological states in the 2 groups prior to randomization but also mitigates the risk of functional unblinding because of subjects not tolerating study drug during samidorphan initiation. Both open-label periods (olanzapine and ALKS 3831) will allow investigators to address tolerability issues prior to randomization.

For all subjects, the once-daily olanzapine dose level throughout the study will be determined individually by the principal investigator (PI) or designee according to current clinical practice.

6. OBJECTIVES

6.1. Primary Objective

To evaluate the efficacy of olanzapine coadministered with samidorphan (ALKS 3831) compared with olanzapine coadministered with placebo in schizophrenia with alcohol use disorder (AUD)

6.2. Secondary Objective

The secondary objective of this study is to evaluate the safety and tolerability of ALKS 3831 in schizophrenia with AUD.

7. SELECTION AND WITHDRAWAL OF SUBJECTS

7.1. Subject Inclusion Criteria

Each subject must meet all of the following inclusion criteria at screening, unless otherwise specified, to be qualified to participate in this study:

1. Is between 18 and 65 years of age, inclusive
2. Is willing and able to provide informed consent
3. Is willing and able to follow the study procedures as outlined in the protocol
4. Is fluent in the language (oral and written) in which assessments will be made and can be reliably rated
5. Has a body-mass index between 18.0 and 40.0 kg/m², inclusive, at screening and Visit 2
6. Meets criteria for schizophrenia according to DSM-IV-TR as confirmed by the MINI administered by qualified site staff
7. Meets criteria for AUD according to DSM-5 as confirmed by the C-VISA and the MINI 7.0 AUD module administered by qualified site staff
8. Has experienced an acute exacerbation of schizophrenia within the past 6 months prior to screening that meets at least 1 of the following criteria:
 - a. Was hospitalized (involuntarily or voluntarily) for symptoms of schizophrenia
 - If applicable, the total duration of any hospitalization(s) within the 30 days prior to Visit 2 must be ≤7 days.
 - b. Committed deliberate self-injury, engaged in aggressive behavior, or displayed signs of suicidal or homicidal ideation deemed clinically significant by the PI
 - c. Was prescribed 1 of the following changes in antipsychotic medication:
 - An increase in antipsychotic dose level due to symptom worsening
 - Change in antipsychotic due to symptom worsening
 - d. Visited the emergency room or an outpatient healthcare facility (involuntarily or voluntarily) due to worsening of psychotic symptoms
9. Meets the following clinical criteria at screening* and Visit 2:
 - a. Has a total Positive and Negative Syndrome Scale (PANSS) score between 50 and 90, inclusive
 - b. Has a score of ≤4 for all of the following PANSS Positive (P) Scale or General Psychopathology (G) items:
 - P1 (delusions)
 - P2 (conceptual disorganization)
 - P3 (hallucinatory behavior)

- P6 (suspiciousness/persecution)
 - P7 (hostility)
 - G8 (uncooperativeness)
- c. Has a Clinical Global Impression-Severity (CGI-S) score ≤ 4
- * A subject who initiated olanzapine treatment during a recent hospitalization for an acute exacerbation (discharged within 2 weeks prior to screening) is not required to meet these criteria at screening, but is required to meet them at Visit 2.
10. In the opinion of the PI or designee, the subject is not a danger to himself/herself or others and has no elevated suicidal ideation or behavior at the time of screening and the subject answers “No” to items #4 and #5 of the Columbia Suicide Severity Scale (C-SSRS) for ideation and behavior in the 30 days prior to screening and Visit 2.
- Although a recent exacerbation of symptoms is needed for inclusion in the study and suicidal behavior may qualify as an exacerbation, a subject who still represents a danger to him/herself at the time of screening is not eligible for this study.
11. Has experienced at least 10 drinking days (a day in which the subject had at least 1 standard alcoholic drink) within the 30 days prior to screening (as assessed by Timeline Follow-Back [TLFB] self-report using the TLFB definition for a standard drink)
- At least 2 of these drinking days must be heavy drinking days, defined as 4 drinks in 1 day for women or 5 drinks in 1 day for men.
12. In accordance with the locally approved informed consent form (ICF), subjects at some sites may be required to have an informant or caregiver who meets some or all of the following criteria:
- a. Informant or caregiver will be in contact with the subject several times per week.
 - b. If necessary, the informant or caregiver will accompany the subject to visits.
 - c. Informant or caregiver will help ensure maximum subject adherence to study procedures.
 - d. The informant or caregiver must be willing and able to provide informed consent by signing the caregiver ICF.
- In Bulgaria, subjects are required to have an informant or caregiver who meets criteria 12a, 12b, 12c and 12d.
13. Agrees to use an acceptable method of contraception for the duration of the study unless surgically sterile or postmenopausal

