7.2. Subject Exclusion Criteria

A subject meeting any of the following criteria at screening, unless otherwise specified, will not qualify for participation in this study:

1. Is pregnant (as indicated by self-report or a positive pregnancy test), planning to become pregnant during the study, or breastfeeding at screening or Visit 2

2. Is investigator-site personnel or is employed by Alkermes, PPD (permanent, temporary contract worker, or designee responsible for the conduct of the study), or other third-party agents of this study or is immediate family of investigator-site personnel or an Alkermes, PPD or other third-party agents at screening or Visit 2
 - Immediate family is defined as a spouse, parent, child, or sibling, whether biological or legally adopted
3. Had his/her first lifetime psychotic episode less than 1 year before screening or has experienced only a single lifetime psychotic episode
4. Has a known or suspected intolerance, allergy, or hypersensitivity to olanzapine at screening or Visit 2
5. Has current or pending legal charges with the potential for incarceration that could interfere with study scheduling at screening or Visit 2
6. Has had significant blood loss (>500 mL) or has donated blood or blood components within 2 months prior to screening or Visit 2
7. Is currently participating in or has participated in a clinical trial of an investigational product (drug, device, or biologic) within the 12 months prior to screening, has participated in more than 2 clinical trials within the 4 years prior to screening, or has ever participated in a samidorphan clinical trial
8. Has a history or current evidence at screening or Visit 2 of a clinically significant condition or abnormality that in the PI's (or designee's) opinion could interfere with subject safety or complicate treatment, such as (but not limited to) the following:
 - Clinically significant renal insufficiency
 - Human immunodeficiency virus (HIV)
 - Hepatitis B
 - Hepatitis C
 - Severe alcohol withdrawal, as indicated by abrupt cessation of alcohol intake followed by seizures, delirium tremens, or other severe withdrawal symptoms per investigator judgment
 - Narrow-angle glaucoma (diagnosis or risk), or any other disease or condition described as a contraindication in the local Zyprexa[®] label
9. Has or has had a malignant tumor within the 5 years prior to screening excluding dermal squamous cell carcinoma, basal cell carcinoma, and cervical carcinoma in situ

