8. STUDY DESIGN

[figure not shown]
This is a Phase 2, multicenter, randomized, double-blind, placebo-controlled study designed to evaluate the efficacy, safety, and tolerability of ALKS 3831 in schizophrenia with AUD. Subjects experiencing disease symptom exacerbation (eg, inpatient hospitalization) within the past 6 months will be considered for screening. Assessment of eligibility is based on DSM-IV-TR diagnosis of schizophrenia and DSM-5 diagnosis of AUD (supported by the subject's medical history, subject self-report, and caregiver or informant report of medical history and/or drinking behavior and confirmed via the MINI and C-VISA). Subjects must also meet certain clinical criteria at screening and prior to randomization. These criteria include (but are not limited to) having a PANSS score between 50 and 90 (inclusive) at screening and Visit 2 and between 50 and 80 (inclusive) at Visit 6 and Visit 8; a PANSS item score of ≤ 4 on Positive (P) Scale and General Psychopathology (G) items P1, P2, P3, P6, P7, and G8; and a CGI-S score ≤ 4 at screening, Visit 2, Visit 6, and Visit 8. Subjects who do not meet PANSS or CGI-S criteria at screening but were prescribed olanzapine during a recent hospitalization (discharged within the 2 weeks prior to screening) may be eligible for the study if they meet symptom severity criteria at Visit 2, Visit 6, and Visit 8. Other eligibility criteria assessed between screening and randomization are ECG (Visit 2) and drug screening (Visit 6) criteria. Complete eligibility criteria are given in [Section 7.1](#) and [Section 7.2](#), and randomization criteria are given in [Section 7.3](#).

All study visits will be outpatient visits. The olanzapine dose level throughout the study will be determined individually by the PI according to current clinical practice.

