Subjects who are taking an antipsychotic other than olanzapine or no antipsychotic medication at Visit 2 will be tapered off of current medication (if applicable) and titrated onto olanzapine beginning at Visit 2 (see [Figure 1](#)) according to a schedule determined by the investigator in accordance with current clinical practice. Subjects who are already taking olanzapine will take their medication as currently prescribed at Visit 2 and for a period of 4 weeks (Visits 3–5) prior to initiation of ALKS 3831 (Visit 6). After Visit 2, all subjects will return to the clinic weekly for dose adjustment, as necessary (permitted at Visits 3 and 4 only), and safety monitoring (Visits 3–5). A cross-taper period of up to 3 weeks is expected when switching to olanzapine and optimizing olanzapine dose.

Unless a change in olanzapine dose is medically indicated, it will remain fixed for the remainder of the study after Visit 5. An increase in dose between Visit 5 and randomization may be a reason for withdrawal from the study, and an increase in dose after randomization is considered an EEDS (see [Section 11.1](#)). A decrease in dose is always allowed when medically indicated. If a dose reduction occurs after randomization, any subsequent dose must be greater than the dose at randomization for this increase to be considered an EEDS.

Figure 1: ALK3831-401 Study Schematic

Abbreviation: V = Study Visit; ALKS 3831=olanzapine plus samidorphan

At Visit 6, subjects will begin a 2-week open-label ALKS 3831 (olanzapine [fixed-dose] coadministered with samidorphan [10 mg]) treatment period. Subjects who do not tolerate ALKS 3831 during this open-label period may be discontinued from the study prior to randomization.

At Visit 8, subjects will be randomized in a 1:1 fashion to 1 of 2 treatment groups and will begin a double-blind treatment period. The 2 treatment groups are as follows:

- ALKS 3831: (ie, olanzapine [dose determined by the PI] plus samidorphan [10 mg])
- Olanzapine (dose determined by the PI) plus placebo

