Dispense Emergency Treatment Card						X	
Confirm Subject's Possession of Emergency Treatment Card							X

¹ Subject and informant/caregiver informed consent (when the latter is required)

² The criteria assessed at these visits are limited to PANSS, CGI-S, and drug screen; see [Section 7.3](#).

³ Full physical examination at screening; brief physical examination at all other scheduled time points

⁴ At each visit, PANSS should be administered before any other clinical assessment

⁵ CGI-S only at this visit, as administered using the Structured Interview Guide for Global Impressions

⁶ The subject should be assisted by the same person each time he or she is asked to complete the TLFB and this person should not conduct the subject's supportive counseling sessions.

⁷ At screening, the "Baseline/Screening" version will be administered for assessing lifetime ideation and behavior, as well as ideation and behavior in the past 30 days. At all other visits, the "Since Last Visit" version will be administered.

⁸ Orthostatic measures should not be completed at screening.

⁹ Thyroid stimulating hormone and carbohydrate deficient transferrin are assessed at screening only; Hemoglobin A1c (HbA_{1c}) is assessed at screening and Visit 2 only.

¹⁰ Height at screening only

¹¹ The recommended time of dosing for subjects is in the evening or at bedtime.

Table 2: Schedule of Visits and Assessments for Double-blind Treatment Period (Visit 8-Visit 26)

	Double-blind Placebo-controlled Treatment																		
Study Visit	8	9	10	11	12	13	14	15	16	17	18	19	20	21	22	23	24	25	26 ¹
Study Week	3	5	7	9	11	13	15	17	19	21	23	25	27	29	31	33	35	37	39
Qualification/Diagnostic Assessments																			
Eligibility Criteria Review ²	X																		
Qualification/Efficacy Measures																			
PANSS ³	X	X	X		X		X		X		X		X		X		X		X
CGI-S and CGI-I	X		X		X		X		X		X		X		X		X		X
TLFB ⁴	X	X	X		X		X		X		X		X		X		X		X
Cigarette Use Question	X	X	X				X						X						X
VAS Desire for Alcohol	X		X		X		X		X		X		X		X		X		X
PSP	X						X						X						X
Exacerbation of Disease Criteria Review		X	X		X		X		X		X		X		X		X		X
AIMS	X		X		X		X		X		X		X		X		X		X
SAS	X		X		X		X		X		X		X		X		X		X
BARS	X		X		X		X		X		X		X		X		X		X
Safety Assessments																			
AE Monitoring	X	X	X		X		X		X		X		X		X		X		X
C-SSRS ⁵	X	X	X		X		X		X		X		X		X		X		X
Concomitant Medications	X	X	X		X		X		X		X		X		X		X		X
Medical History ⁶	X	X	X		X		X		X		X		X		X		X		X

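### Criterion 10 does not bar suicidal behavior arising between screening and Visit 2: its Visit 2 test uses C-SSRS ideation items only, and its behavior wording is tied to screening

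*Protocol*

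**What the plan says.** Inclusion criterion 10 (Protocol Section 7.1) has two limbs and a sub-bullet.

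- **PI-opinion limb.** The PI or designee must judge that the subject is not a danger to self or others and "has no elevated suicidal ideation or behavior at the time of screening".
- **C-SSRS limb.** The subject must answer No to "items #4 and #5 of the Columbia Suicide Severity Scale (C-SSRS) for ideation and behavior in the 30 days prior to screening". The sentence continues and names Visit 2 too.
- **Sub-bullet.** Suicidal behavior may be the qualifying exacerbation, but "a subject who still represents a danger to him/herself at the time of screening is not eligible for this study".

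Table 1 (Section 8.2) schedules the C-SSRS at screening (Baseline/Screening form) and at Visit 2 (Since Last Visit form). Footnote 2, attached to the eligibility review at Visits 2 and 6, says: "The criteria assessed at these visits are limited to PANSS, CGI-S, and drug screen". After the PANSS and CGI-S limits, the Section 8 summary adds: "Other eligibility criteria assessed between screening and randomization are ECG (Visit 2) and drug screening (Visit 6) criteria". Visit 2 is also where treatment starts. Subjects who are not already on olanzapine "will be tapered off of current medication (if applicable) and titrated onto olanzapine beginning at Visit 2".

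**The concern.** Criterion 10 mentions both ideation and behavior and both visits, so a reader would expect it to cover all four combinations. Behavior at Visit 2 appears to be missing.

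What is at stake is patient safety. All visits are outpatient, and Visit 2 is when medication is being changed. Inclusion 8b accepts self-injury or clinically significant suicidal ideation in the previous 6 months as the qualifying exacerbation, so candidates with recent suicidal acts are foreseeable. It would be odd for ideation with intent to meet an explicit bar at Visit 2 while an actual attempt meets none.

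**Working it through.** Apart from the length of the interval, this is a comparison of texts.

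**1. What items 4 and 5 test.** On both forms in Appendix K, the two items are headed as active suicidal ideation: item 4 with some intent, item 5 with a plan and intent. SAP Section 3.8.7, Table 7, also lists them under ideation. Actual, interrupted and aborted attempts and preparatory acts sit in a separate, unnumbered behavior section, which criterion 10 does not cite.

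**2. What each limb reaches.**

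- Ideation at screening: both limbs.
- Behavior at screening: the PI-opinion limb.
- Ideation at Visit 2: the C-SSRS limb.
- Behavior at Visit 2: neither limb.

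Section 7.1 makes screening the default timing unless a criterion says otherwise. Eleven of the other entry criteria name Visit 2 explicitly (inclusions 5, 8a and 9; exclusions 1, 2, 4, 5, 6, 8, 10 and 21). The PI-opinion limb does not. Section 7.3 has no suicidality criterion at randomization.

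**3. Whether the pathway can occur.** On both forms, questions 3 to 5 are asked only if question 2 is Yes. If questions 1 and 2 are both No, the rater goes straight to the behavior section. There the rater may infer intent that the subject denies and record an actual attempt. Such a subject has no Yes on item 4 or 5. I assume a site would treat unasked items as No.

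**4. Length of the interval.** Table 1 puts screening at Day -59 to -29 and Visit 2 at Day -28.

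- Shortest: -28 - (-29) = 1 day.
- Longest: -28 - (-59) = 31 days.

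These are nominal days, before the ±2-day visit window. The screening form looks back 30 days, so the two forms together cover 1 + 30 = 31 to 31 + 30 = 61 days before Visit 2. The information is collected, but criterion 10 does not use the behavior part of it at Visit 2.

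**5. What else applies at Visit 2.**

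- Inclusion 9 requires PANSS total 50 to 90, six items at 4 or below, and CGI-S at 4 or below. The PANSS interview asks about self-harm and attempts, but under the depression item (G6), which is not one of the six capped items. The CGI-S guide covers the past 7 days, so in the longest interval 31 - 7 = 24 days fall outside it.
- Inclusion 8a caps hospital stay at 7 days in the 30 days before Visit 2.
- Exclusion 8 begins "Has a history or current evidence at screening or Visit 2 of a clinically significant condition or abnormality" and rests on PI opinion. It does not name suicidality.
- Section 7.4 allows discontinuation at any time in the subject's interest.

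The MINI, whose suicidality module covers the past month, is done at screening only.

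**6. Operational text.** Neither footnote 2 nor the Section 8 summary lists the C-SSRS among the Visit 2 checks, although criterion 10 requires items 4 and 5 there.

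**The case against.** **Visit 2 is not unguarded.** A reader might infer that only discretion remains there. The documents do not support that: the PANSS, CGI-S and hospital-stay limits are mandatory. Exclusion 8 also becomes mandatory once the PI forms the opinion, and the PI or designee completes the C-SSRS, so a recorded act would be seen. This stands and limits the point. Still, none of these provisions is specific to behavior, and an act can pass all of them.

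**The time of screening may mean a period.** Table 1 gives screening a range of days, the Synopsis allows up to 30 days for it, and exclusion 12 uses the word as a period. On that reading the PI-opinion limb runs to Day -29 and the gap nearly closes. The reading is arguable. Against it, other criteria name both visits when both are meant. Visit 2 is also a separate open-label visit, and its C-SSRS is the form that would record an act in the interval.

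**Screening is covered.** A reader might infer that criterion 10 ignores behavior altogether. It does not. The PI-opinion limb names behavior at screening and is informed by the C-SSRS and the MINI. The phrase about ideation and behavior may only describe the form's look-back, since Table 1 footnote 7 says "as well as ideation and behavior in the past 30 days". It is also tempting to ask for a fixed 30-day bar on behavior before screening. The sub-bullet deliberately admits such behavior as an exacerbation and asks whether the danger persists, so a fixed bar would be a trade-off and is not needed to close the Visit 2 gap.

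**The footnote is loose.** It pools Visits 2 and 6, lists a drug screen not scheduled at Visit 2, and also omits the Visit 2 BMI and ECG criteria. Table 1 places the C-SSRS at Visit 2 under qualification and safety assessments, and Section 8 defers to Sections 7.1 and 7.2 for the complete criteria. The omission is therefore a wording mismatch, and does not show that the C-SSRS is skipped.

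**Conclusion.** The point holds for behavior at Visit 2. As written, a suicidal act between screening and Visit 2, recorded on the Since Last Visit form with No on items 4 and 5, meets criterion 10. Entry then depends on provisions not written for suicidality.

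The window is nominally up to 31 days, and less if screening is read as the whole period. The number of subjects affected is not in the documents. It is probably small, because a C-SSRS attempt implies some wish to die and many attempters would answer Yes to item 4 or 5. Sample size, error rates and efficacy analyses are unaffected. This is a cheap improvement to a safety rule.

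**What to change.** (a) In the PI-opinion limb and its sub-bullet, replace *at the time of screening* with *at screening and Visit 2*. In the sub-bullet, which is worded as a bar, *or* is the safer conjunction.

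(b) For Visit 2 only, add to the C-SSRS limb: *and no actual, interrupted or aborted attempt or preparatory acts recorded since screening in the C-SSRS Suicidal Behavior section*. Leave behavior before screening to the PI judgment that the sub-bullet already sets.

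(c) Add the C-SSRS to Table 1 footnote 2 for Visit 2 and to the Section 8 summary of later eligibility checks, so that both match criterion 10.

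The cost is two edits in criterion 10, one footnote, one summary sentence and the eligibility checklist. No assessment is added, because the C-SSRS is already done at Visit 2. The downside is that a few candidates with a suicidal act between screening and Visit 2 would be screened out or delayed.

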7.2. Subject Exclusion Criteria

A subject meeting any of the following criteria at screening, unless otherwise specified, will not qualify for participation in this study:

1. Is pregnant (as indicated by self-report or a positive pregnancy test), planning to become pregnant during the study, or breastfeeding at screening or Visit 2

2. Is investigator-site personnel or is employed by Alkermes, PPD (permanent, temporary contract worker, or designee responsible for the conduct of the study), or other third-party agents of this study or is immediate family of investigator-site personnel or an Alkermes, PPD or other third-party agents at screening or Visit 2
 - Immediate family is defined as a spouse, parent, child, or sibling, whether biological or legally adopted
3. Had his/her first lifetime psychotic episode less than 1 year before screening or has experienced only a single lifetime psychotic episode
4. Has a known or suspected intolerance, allergy, or hypersensitivity to olanzapine at screening or Visit 2
5. Has current or pending legal charges with the potential for incarceration that could interfere with study scheduling at screening or Visit 2
6. Has had significant blood loss (>500 mL) or has donated blood or blood components within 2 months prior to screening or Visit 2
7. Is currently participating in or has participated in a clinical trial of an investigational product (drug, device, or biologic) within the 12 months prior to screening, has participated in more than 2 clinical trials within the 4 years prior to screening, or has ever participated in a samidorphan clinical trial
8. Has a history or current evidence at screening or Visit 2 of a clinically significant condition or abnormality that in the PI's (or designee's) opinion could interfere with subject safety or complicate treatment, such as (but not limited to) the following:
 - Clinically significant renal insufficiency
 - Human immunodeficiency virus (HIV)
 - Hepatitis B
 - Hepatitis C
 - Severe alcohol withdrawal, as indicated by abrupt cessation of alcohol intake followed by seizures, delirium tremens, or other severe withdrawal symptoms per investigator judgment
 - Narrow-angle glaucoma (diagnosis or risk), or any other disease or condition described as a contraindication in the local Zyprexa[®] label
9. Has or has had a malignant tumor within the 5 years prior to screening excluding dermal squamous cell carcinoma, basal cell carcinoma, and cervical carcinoma in situ
10. Has clinically significant hypotension or hypertension not stabilized by medical therapy; a clinically significant cardiac arrhythmia, cardiomyopathy, or cardiac conduction defect; or has a clinically significant ECG abnormality at screening or Visit 2, including (but not limited to) the following:
 - For men, QT interval (corrected using the Fridericia formula; QTcF) >450 milliseconds

- For women, QTcF >470 milliseconds
11. Has a history of a myocardial infarction or unstable angina, including a silent myocardial infarction discovered on ECG
12. Has a positive drug screen at screening for opiates (including buprenorphine, norbuprenorphine, codeine, hydrocodone, hydromorphone, methadone, morphine, oxycodone, and oxymorphone) or meets criteria for any of the following medication restrictions:
- Has taken opioid agonists (eg, codeine, oxycodone, tramadol, or morphine) within 14 days prior to screening or anticipates needing to take opioid medication during the study period (eg, planned surgery)
 - Has taken opioid antagonists within 60 days before screening
 - Has received a long-acting formulation of any antipsychotic medication by intramuscular injection within 2 months prior to screening
 - Long-acting formulations of antipsychotics are also prohibited medications; therefore, administration should not occur or be planned to occur during screening (see [Section 8.4.2](#))
 - Has received clozapine for more than 1 week during the past year
 - Has used naltrexone (including ReVia[®]/Depade[®] and Vivitrol[®]) within 2 months prior to screening; naloxone, acamprosate (Campral[®]), disulfiram (Antabuse[®]), or other medication for alcohol dependence within 14 days prior to screening; or has been admitted to an alcohol detoxification program within the past 3 months (including current treatment at screening)
 - Is currently taking an antidepressant unless the subject has been on a stable dose for at least 30 days prior to screening and it is anticipated that the dose will not change during the subject's participation in the study. The medical monitor should be contacted with any questions about the appropriateness of including a subject taking an antidepressant medication. Antipsychotic use for depression is exclusionary.
 - Is currently receiving treatment with a hypoglycemic agent (eg, metformin, insulin, sulfonylurea, etc)
 - Has used an inducer or moderate to strong inhibitor of CYP3A4 (prescription medications, over-the-counter medications, or dietary supplements) within 30 days before screening. See [Appendix L](#) for a partial list of prohibited CYP3A4 inducers and moderate to strong inhibitors.
 - Is currently using or anticipates needing to use a prohibited medication or substance anytime during the study period (see [Section 8.4.2](#) and [Section 8.4.3](#))

13. Have any of the following psychiatric conditions per DSM-IV-TR criteria, unless otherwise specified, as assessed by the MINI (if possible). Conditions not assessable by the MINI should be assessed by clinical judgment or the C-VISA (if applicable):
 - a. Clinically significant cognitive difficulties including dementia, delirium, or amnesic syndromes, or any other cognitive disorder present within the past 2 years that, in the opinion of the PI or designee, could interfere with participation in the study (ie, could potentially compromise subject safety or adversely affect the evaluation of efficacy)
 - b. Substance use disorders other than AUD within the past 1 year as defined by DSM-5 criteria for the following:
 - Hallucinogen-related disorder
 - Inhalant-related disorder
 - Opioid-related disorder
 - Sedative-, hypnotic-, or anxiolytic-related disorder
 - Stimulant-related disorder
 - c. Any other psychiatric condition within the past 1 year that could, in the PI's or designee's opinion, interfere with participation in the study, especially Axis I (according to DSM-IV-TR criteria) disorders; established or confirmed diagnosis of schizoaffective disorder or bipolar disorder; or current, untreated, or unstable major depressive disorder
 - Subjects with current but stable depression, depressive symptoms, or major depressive disorder may be eligible provided schizoaffective disorder has been ruled out.
14. Is planning a significant change in caffeine use or is planning to enter a smoking cessation program
15. Has a history of neuroleptic malignant syndrome, has a history of clinically significant extrapyramidal symptoms when taking olanzapine, or has had clinically significant tardive dyskinesia or tardive dystonia within 30 days of screening
16. Has unstable thyroid dysfunction within the 6 months prior to screening (eg, hypothyroidism, hyperthyroidism, or thyroiditis that was untreated or was discovered and resulted in treatment within the 6 months prior to screening) or a thyroid stimulating hormone (TSH) level higher than 10% above the upper limit of the normal range at screening.
17. Has a neurologic condition, including (but not limited to) the following:
 - History of seizure disorder or a condition associated with seizures (excluding febrile seizures but including seizures associated with substance use or withdrawal) within the past 6 months
 - History of brain tumor, subdural hematoma, or other clinically significant neurological condition within the 1 year prior to screening
 - Head trauma with a loss of consciousness within 30 days prior to screening

- An active acute or chronic central nervous system infection
 - History of stroke or cerebrovascular infarction
18. Has dyslipidemia (total cholesterol >280 mg/dL or triglycerides >500 mg/dL at screening)
19. Has diabetes or meets any of the following criteria at screening:
- Hemoglobin A1c (HbA_{1c}) ≥6.5%
 - A random plasma glucose ≥200 mg/dL (11.1 mmol/L)
20. Has a laboratory abnormality at screening, including (but not limited to) the following (clinical laboratory assessments may be repeated if the PI feels the test may be in error):
- Aspartate aminotransferase or alanine aminotransferase value ≥3 times the upper limit of the laboratory normal reference range
 - Absolute neutrophil count ≤1.5 × 10³ per μL
 - Platelet count ≤75 × 10³ per μL
 - Serum creatinine >2.5 mg/dL
21. Has no living arrangements available at screening or Visit 2, consistently lacks or loses housing (such that maintaining contact with the subject will be difficult), or has plans to leave the study site area during the study period
- A temporary loss of living arrangements due to loss of caregiver support or other circumstances (eg, recent symptom exacerbation) is allowed if housing is typically available when schizophrenia and AUD symptoms are stable and not exacerbated.

